- Investigators may gently remove an obstacle that is blocking the ear canal if it prevents IP application or causes subjects to experience an uncomfortable sensation. If the obstacle is adherent to the tympanic membrane, it should not be removed; it is recommended to wait until the obstacle comes off.
- Subjects should refrain from activities that can increase the middle ear pressure including plane travel (at least 28 days after IP application), positive pressure ventilation (e.g., CPAP or BiPAP) devices, Valsalva maneuvers, excessive high-pressure nose blowing, or diving underwater.
- Subject must refrain from activities that can excessively increase body temperature (e.g. Sauna) for at least 3 days after IP application.
- Subject must refrain from activities that stimulate sweating excessively for at least 3 days after IP application.

Duration of Treatment:

SAD and single dose expansion: Topical application into the affected ear on Day 1.

MAD: Topical application into the affected ear on Days 1, 15, and 29.

Multiple Dose Expansion: Topical application into the affected ear on Day 1 and if the subject has not achieved complete closure of the TMP at Day 15 and Day 29, additional treatment will occur. If the subject achieves complete closure on either Day 15 or Day 29, no additional treatment is required at those visit(s).

Treatment Discontinuation Criteria:

SAD and single dose expansion

Not applicable because there is a single treatment of ASP0598 Otic Solution or placebo.

MAD and multiple dose expansion

Treatment Discontinuation

During the course of IP administration, if the subject experiences a drug-related adverse event (AE), the IP administration may be discontinued at the investigator's discretion.

In addition, IP administration will be discontinued if severe intensity occurs in any of the following situations:

- Subject develops cholesteatoma or suspicion of neoplasm in the treated ear as determined by the investigator.
- Subject develops suspected ototoxicity symptoms (e.g., sudden hearing loss at high frequencies (1, 2, 4 kHz), new high frequency tinnitus or new balance disorder) which are considered by the investigator to be related to the study drug.
- Subjects with persistent otitis media or otitis externa unresponsive to oral and topical antibiotics (as described in Previous and Concomitant Treatment [Medication and Nonmedication Therapy of the synopsis and protocol Section 6.5])

Dose Escalation:

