- c. AEs will be collected from the time of informed consent through Day 85 or EOS. Any AEs ongoing at Day 85 or EOS Visit must be followed until resolution or investigator determines the event to be stable. AEs should be assessed at least monthly.
- d. ASP0598 Otic Solution or placebo will be applied onto the remaining tympanic membrane under a microscope with a 22-gauge blunt needle. After ASP0598 Otic Solution or placebo administration, subjects will be required to remain on their side with the treated ear facing up for at least 15 minutes. Please see the Pharmacy Manual, Section 9.4: Dose Administration for detailed instructions.
- e. Otology examinations will be performed for both ears at the screening visit.
- f. Days 1, 15 and 29, microscopic ear examination will be performed prior to and 60 (± 5) minutes after ASP0598 Otic Solution/placebo administration. Skin local reaction at the application site will be evaluated by Modified Brighton Grading Scheme (Appendix 12.9) at 60 (± 5) minutes after ASP0598 Otic Solution/placebo administration.
- g. Ear cleaning will not be conducted between Days 2 – 57, unless it is absolutely necessary. Investigators will not clean the treated ear by suctioning unless subjects experience uncomfortable ear discharge).
- h. At Days 1, 15, and 29, imaging pictures will be taken at the following time points: pre-dose, immediately after, 30 (± 5) minutes, and 60 (± 5) minutes after the ASP0598 Otic Solution or placebo administration.
- i. At Day 85 and/or EOS, the whole TM should be visible before taking imaging picture. If the whole TM is not visible, the investigator should clean the ear canal.
- j. Bone conduction testing at Day 8, 15, 22, 29, 36 and 57 will be tested only at 1, 2 and 4 kHz (ototoxicity assessment).
- k. Urine or serum pregnancy test will be performed in women of childbearing potential.
- l. Day 1 and Day 29, PK blood draw will be performed at the following time points: pre-dose (-15) minutes, 30 (± 5) minutes and 60 (± 5) minutes after ASP0598 Otic Solution or placebo administration into the affected ear.

Table 5 Schedule of Assessments – Multiple Dose Expansion

| | Day | Screening | Randomization | Observation | | | | | |
|---|------|--------------------|----------------|------------------|------------------|----------------|----------------|----------------|-------------------------------|
| | | Day – 28 to Day -1 | Day 1 | Day 15 | Day 29 | Day 43 | Day 57 | Day 85 | Day 113 Last Visit/ EOS |

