5.1 Inclusion Criteria

A subject is eligible for the study if all the following apply:

1. Institutional Review Board (IRB)/Independent Ethics Committee (IEC) approved written Informed Consent and privacy language as per national regulation (e.g., Health Insurance Portability and Accountability Authorization for US sites) must be obtained from the subject or legally authorized representative prior to any study-related procedures (including withdrawal of prohibited medication, if applicable).
2. Subject must be 18 to 75 years of age at the time of informed consent.
3. Subject has chronic tympanic membrane perforation (CTMP) documented as persisting longer than 3 months.
4. A female subject is eligible to participate if she is not pregnant see Appendix [12.3: Contraception Requirements](#) and at least one of the following conditions applies:
 - a. Not a woman of childbearing potential (WOCBP) as defined in Appendix [12.3: Contraception Requirements](#) OR
 - b. WOCBP who agrees to follow the contraceptive guidance as defined in Appendix [12.3: Contraception Requirements](#) starting at screening and for at least 28 days after investigational product (IP) application.
5. Female subject must agree not to breastfeed starting at drug application on Day 1 and for at least 28 days after IP application.
6. Female subject must not donate ova starting on Day 1 and for at least 28 days after IP application.
7. A male subject with female partner(s) of child-bearing potential must agree to use contraception starting on Day 1 and for at least 28 days after IP application as detailed in Appendix [12.3](#).
8. A male subject must not donate sperm starting on Day 1 and for at least 28 days after IP application.
9. Male subject with a pregnant or breastfeeding partner(s) must agree to remain abstinent or use a condom from Day 1 and for at least 28 days after IP application.
10. Subject must be willing and able to comply with the study requirements including refraining from using prohibited concomitant medications.
11. Subject agrees not to participate in another interventional study during the study period.

12. Subject has the ability to understand and the willingness to sign a written informed consent document.

Waivers to the inclusion criteria will NOT be allowed.

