6.4 Investigational Product Compliance

Single Dose

IP will be administered by the PI or designee on Day 1. Ensure the final IP Otic Solution is administered within the appropriate window of time, depending on the assigned treatment. Refer to the Pharmacy Manual, Section 9.3, for detailed information. Subjects will be provided Ear Care Recommendations (Appendix 12.8) that must be reviewed and acknowledged on Day 1 in the source document. The subject should follow this guidance for the duration of their participation. The investigator will examine the treated ear at every visit.

Multiple Dose

IP will be administered by the PI or designee on Days 1, 15, and 29. Ensure the final IP Otic Solution is administered within the appropriate window of time, depending on the assigned treatment. Refer to the Pharmacy Manual, Section 9.3, for detailed information. Subjects

will be provided Ear Care Recommendations (Appendix 12.8) that must be reviewed and acknowledged at each IP administration visit in the source document. The subject should follow this guidance for the duration of their participation. The investigator will examine the treated ear at every visit.

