12.3 Contraception Requirements

WOCBP who are eligible for participation in the study, including those who choose complete abstinence, must have pregnancy tests as specified in the schedule of assessments. Pregnancy test results must confirm that the subject is not pregnant.

WOMEN OF CHILDBEARING POTENTIAL DEFINITIONS AND METHODS OF CONTRACEPTION DEFINITIONS

A female is considered fertile (i.e., WOCBP) following menarche and until becoming postmenopausal unless permanently sterile.

Females in the following categories are not considered WOCBP

- Premenarchal
- Premenopausal with 1 of the following (i.e., permanently sterile):
 - Documented hysterectomy
 - Documented bilateral salpingectomy
 - Documented bilateral oophorectomy
- Postmenopausal

A postmenopausal state is defined as at least 12 months after last menstrual bleeding without an alternative medical cause.

In case the last menstrual bleeding cannot be clearly determined, confirmation with more than 1 follicle-stimulating hormone (FSH) measurement of at least > 40 IU/L (or higher per local institutional guidelines) is required.

Females on hormone replacement therapy (HRT) and whose menopausal status is in doubt will be required to use 1 of the nonestrogen hormonal highly effective contraception methods if they wish to continue their HRT during the study. Otherwise, they must discontinue HRT to allow confirmation of postmenopausal status by repeated FSH measurements before study enrollment.

Documentation of any of these categories can come from the study site personnel's review of the female subject's medical records, medical examination or medical history interview.

CONTRACEPTION GUIDANCE FOR FEMALE SUBJECTS OF CHILDBEARING POTENTIAL

Female subjects of childbearing potential are eligible for participation in the study if they agree to use 1 of the highly effective methods of contraception listed below from the time of signing the ICF and until the end of relevant systemic exposure, defined as 28 days after the IP application.^a

Highly effective methods of contraception (failure rate of $< 1\%$ per year when used consistently and correctly)^b:

- Combined (estrogen- and progestogen-containing) hormonal contraception associated with inhibition of ovulation

- Oral
- Intravaginal
- Transdermal
- Progestogen-only hormonal contraception associated with inhibition of ovulation
 - Oral
 - Injectable
 - Implantable
- Other combined (estrogen- and progesterone-containing) methods
 - Vaginal ring

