 - Injectable
 - Implantable
 - Intrauterine hormone-releasing system or intrauterine device
- Other combined methods
- Vasectomized partner

A vasectomized partner is a highly effective contraception method provided that the partner is the sole male sexual partner of the WOCBP and the absence of sperm has been confirmed. If not, an additional highly effective method of contraception should be used.
- Sexual abstinence

Sexual abstinence is considered a highly effective method only if defined as refraining from heterosexual intercourse during the entire period of risk associated with the test product. The reliability of sexual abstinence needs to be evaluated in relation to the duration of the study and the preferred and usual lifestyle of the subject. It is not necessary to use any other method of contraception when complete abstinence is elected.

^a Local laws and regulations may require use of alternative and/or additional contraception methods.

^b Typical use failure rates may differ from those when used consistently and correctly. Use should be consistent with local regulations regarding the use of contraceptive methods for subjects participating in clinical studies.

CONTRACEPTION GUIDANCE FOR MALE SUBJECTS WITH PARTNER(S) OF CHILDBEARING POTENTIAL.

Male subjects with female partners of childbearing potential are eligible for participation in the study if they agree to the following during treatment and until the end of relevant systemic exposure defined as 28 days after IP application.^a

- Inform any and all partner(s) of their participation in a clinical drug study and the need to comply with contraception instructions as directed by the investigator
- Use a condom
- Female partners of male subjects who have not undergone a vasectomy with the absence of sperm confirmed or a bilateral orchiectomy should consider use of effective methods of contraception

^a Local laws and regulations may require use of alternative and/or additional contraception methods.

12.4 Adverse Events: Definitions and Procedures for Recording, Evaluating, Follow-up and Reporting

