12.4.6 Reporting Procedures for Special Situations

12.4.6.1 Pregnancy

If a female subject becomes pregnant during the study dosing period or within 28 days after IP application on Day 1, the investigator is to report the information to the sponsor according to the timelines in [Section 12.4.5 Reporting Procedures for Serious Adverse Events] using the SAE worksheet or a pregnancy form and in the eCRF.

The investigator will attempt to collect pregnancy information on any female partner of a male subject who becomes pregnant during the study dosing period or within 28 days after IP application on Day 1 from the discontinuation of dosing and report the information to sponsor according to the timelines in [Section 12.4.5 Reporting Procedures for Serious Adverse Events] using the SAE worksheet or pregnancy form.

The expected date of delivery or expected date of the end of the pregnancy, last menstruation, estimated conception date, pregnancy result and neonatal data, etc., should be included in this information.

While pregnancy itself is not considered to be an AE or SAE, any pregnancy complication or termination (including elective termination) of a pregnancy is to be reported for a female subject as an AE in the eCRF or SAE per [Section 12.4.5 Reporting Procedures for Serious Adverse Events]. For (S)AEs experienced by a female partner of a male subject, (S)AEs are to be reported via the SAE worksheet.

Additional information regarding the outcome of a pregnancy when also categorized as an SAE is mentioned below:

- "Spontaneous abortion" includes miscarriage, abortion and missed abortion.
- Death of a newborn or infant within 1 month after birth is to be reported as an SAE regardless of its relationship with the IP.
- If an infant dies more than 1 month after the birth, it is to be reported if a relationship between the death and intrauterine exposure to the IP is judged as "possible" by the investigator.
- Congenital anomaly (including anomaly in miscarried fetus)

Unless a congenital anomaly is identified prior to spontaneous abortion or miscarriage, the embryo or fetus should be assessed for congenital defects by visual examination or other means as appropriate. (S)AEs experienced by the newborn/infant should be reported via the pregnancy reporting form. Generally, follow up will be no longer than 6 to 8 weeks following the estimated delivery date.

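### In the multiple dose parts, the pregnancy reporting window for female subjects is tied to Day 1 and can close up to 28 days before the protocol's own precaution period ends

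*Protocol*

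**What the plan says.** **Reporting.** Section 12.4.6.1 of the protocol opens: "If a female subject becomes pregnant during the study dosing period or within 28 days after IP application on Day 1". In that case the investigator must inform the sponsor on the SAE timeline. The next paragraph, on partners of male subjects, covers the dosing period or "within 28 days after IP application on Day 1 from the discontinuation of dosing". The same section says that pregnancy in itself is neither an AE nor an SAE, but that complications and terminations are to be reported.

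**Dosing.** The Synopsis gives "MAD: Topical application into the affected ear on Days 1, 15, and 29". Section 6.4 says of the multiple dose parts: "IP will be administered by the PI or designee on Days 1, 15, and 29". In multiple dose expansion the Day 15 and Day 29 applications are omitted when closure is confirmed (sections 4.1 and 6.6).

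**Precautions.** Inclusion criterion 4b in section 5.1 requires contraception "starting at screening and for at least 28 days after investigational product (IP) application". Criteria 5 to 9 use the same 28 days for breastfeeding, ova and sperm donation, and male precautions. Appendix 12.3 has female subjects use contraception "until the end of relevant systemic exposure, defined as 28 days after the IP application", and male subjects "during treatment and until the end of relevant systemic exposure defined as 28 days after IP application". Where these passages name Day 1, it is as a start and never as the point from which the 28 days run.

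**Testing.** A footnote to the Schedules of Assessments says "Urine or serum pregnancy test will be performed in women of childbearing potential". After Day 1 the tests fall on Days 57 and 85 in MAD (Table 4) and Days 57 and 113 in multiple dose expansion (Table 5).

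**The concern.** The Day 1 anchor works when there is one application. With three applications two weeks apart, the 28 days counted from Day 1 are used up on the day of the third. The dosing-period limb ends on that day too. The protocol nevertheless treats a 28-day period after application as relevant exposure and asks for precautions during it.

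A pregnancy that begins in that period and proceeds without complication would fall outside the mandatory report, even though a scheduled test on Day 57 or later could detect it. What could be lost is the estimated conception date, the pregnancy result and the neonatal data that section 12.4.6.1 wants collected. This is the first clinical study of the product (section 2.2), so pregnancy data from elsewhere are not available to fill the gap.

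**Working it through.** No sample size, power or error rate is involved. The check is a count of study days.

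**Inputs**
- Reporting: dosing period, or 28 days after the application on Day 1 (12.4.6.1).
- Precautions: 28 days after application (5.1 criteria 4b to 9; Appendix 12.3).
- Nominal applications: Days 1, 15 and 29 (Synopsis; 6.4).
- Variation in the third dose: 3 days either way, as in the MAD visit windows, and 5 days late under the alternate schedule for multiple dose expansion (Table 16).

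**Formulas.** Let L be the study day of the last application.
- Reporting ends on R = max(L, 1 + 28) = max(L, 29).
- Precautions end on C = L + 28, if the 28 days apply to each application.
- Uncovered period G = C − R. This equals L − 1 when L is at most 29, and 28 when L is later.

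**Single dose parts.** L = 1, so R = 29, C = 1 + 28 = 29 and G = 0. The wording is consistent there.

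**Multiple dose parts**

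| Applications given (day) | R | C | G (days) |
|---|---|---|---|
| 1 only | 29 | 29 | 0 |
| 1, 15 | 29 | 15 + 28 = 43 | 14 |
| 1, 15, 26 (third 3 days early) | 29 | 26 + 28 = 54 | 25 |
| 1, 15, 29 (nominal) | 29 | 29 + 28 = 57 | 28 |
| 1, 29 (second skipped) | 29 | 57 | 28 |
| 1, 15, 32 (third 3 days late) | 32 | 32 + 28 = 60 | 28 |
| 1, 15, 34 (third 5 days late) | 34 | 34 + 28 = 62 | 28 |

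On the nominal schedule the uncovered days are Days 30 to 57.

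**Alternative reading of the precautions.** Suppose the 28 days were meant to run from the Day 1 application only. Then C = 29 for everyone and the two windows agree. Precautions would, however, stop on the day of a nominal third application, so the text would still need correcting.

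**Partner sentence.** Counting from Day 1 gives Day 29. Counting from the end of dosing gives 29 + 28 = Day 57 on the nominal schedule. The sentence contains both anchors and does not say which governs.

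**After reconciliation.** If reporting were counted from the last application, R would equal C in every row and G would be 0. The single dose parts would stay at Day 29.

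**The case against.** The strongest reply is that the practical exposure is small and that other provisions catch most of it.

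- Tests on Day 57 and later would detect pregnancies in female subjects. This is true, but detection does not create a duty to report.
- Section 7.3.7 lists pregnancy among the special situations to be communicated to the sponsor, with no 28-day limit of its own. It refers to 12.4.6 for the procedure, so it leads back to the same window.
- Complications and terminations are reportable, and under section 7.3.1 AE collection runs to 14 days after the last visit. This stands. It narrows the gap to uncomplicated pregnancies.
- The animal studies in section 2.1.1 found no discernible systemic exposure. This also stands and keeps the point minor.

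A reader might go further and infer a 28-day gap for all 16 + 39 = 55 multiple dose subjects and their partners. The documents do not support that:

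- Expansion opens only on a committee decision and has 26 subjects if two groups are chosen.
- The total includes women who cannot become pregnant and men, who fall under the partner sentence alone.
- In expansion, a subject whose closure is confirmed may receive only one or two doses, which gives 0 or 14 days when the doses are Day 1 only or Days 1 and 15.
- The partner sentence does not simply repeat the Day 1 anchor. One of its two anchors would leave no gap at all.

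A reader might also take Day 57 as the stated end of contraception. It is not stated: neither 5.1 nor 12.3 says that the 28 days run from the last application.

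**Conclusion.** The point holds as an internal inconsistency. For a female subject in MAD or multiple dose expansion on nominal dosing days, mandatory pregnancy reporting does not reach past Day 29. The uncovered period is 0 to 28 days depending on the doses received, and 28 days in the fully dosed nominal case. It concerns only subjects able to become pregnant who receive a second or third dose. The documents do not allow that number to be counted.

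Two assumptions carry the result:

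- The 28 days in 5.1 and 12.3 apply to each application. This is the natural reading, because those passages do not count the 28 days from Day 1.
- The dosing period means first to last application. The protocol's list of key terms defines the screening, investigational and study periods but not this one. A longer meaning would shrink or close the gap.

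For partners, the finding is that the sentence cannot be applied as written, not that a gap of known length exists. It would also go too far to infer that pregnancies would be missed altogether, given the scheduled tests and the reporting of complications. No endpoint, estimand or analysis in the SAP is affected. The priority is low, but the rule is wrong as written for the multiple dose parts and is worth correcting.

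**What to change.** Reconcile section 12.4.6.1 with section 5.1, Appendix 12.3 and the multiple dose schedule:

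- State one anchor and use it for both the reporting window and the contraception window. Say explicitly which application the 28 days are counted from.
- Make the reporting window cover the whole period that the protocol defines as exposed.
- Define the dosing period, or drop the term.
- Rewrite the partner sentence with a single anchor. Replacing only the Day 1 phrase would leave the clause about the end of dosing attached and the sentence still unusable.

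The sponsor has to decide which precaution period is intended; this review does not propose one. The cost is an amendment to the wording of a safety appendix, the related eligibility text and Appendix 12.3. No dose, visit, test, sample size or analysis needs to change.
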